COVER PAGE

Protocol title: Disease Management Platform for Heart Failure
(DMP-HF)

NCT number: NCT04782973

Document date: 06/17/2021

PRINCIPAL/OVERALL INVESTIGATOR

[name]

PROTOCOL TITLE

A novel disease management platform delivered via smartphone application for the management of patients with heart failure: pilot study

FUNDING

AstraZeneca

VERSION DATE

6/17/2021

I. SPECIFIC AIMS

Specific Aim 1: To test the feasibility of implementing the AMAZE™ disease management platform intervention after in-patient heart failure hospitalization and patient perceived value of the AMAZE™ disease management platform.

Specific Aim 2: [Exploratory] To test whether a digital health platform leads to heart failure symptom changes using the Kansas City Cardiomyopathy Questionnaire (KCCQ), patient daily log compliance, patient app usage, patient app messaging, changes in hospital readmissions and use of ancillary healthcare resources.

II. BACKGROUND AND SIGNIFICANCE**Public Health Significance**

Heart failure (HF) management and readmissions remain at the top of the list of complex topics in cardiovascular medicine, in the United States. The CDC estimates 6.5 million adults in the United States have heart failure and costs in 2012 were approximately 30.7 billion dollars {Benjamin, 2019 #472}. This conversation spans across multiple sectors in our complex healthcare system; involving doctors, administrators, payors, patients and caretakers.

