Current system-wide programs to curb HF-related hospital readmissions have shown inconsistent results. However, outpatient transitional care supportive programs have been linked to improved HF-related outcomes, including reduced hospital readmissions, in small studies. Small studies also indicate that remote transfer of non-invasive data through telemonitoring (e.g., blood pressure and weight) and structured telephone support may reduce hospital readmissions in a cost-effective manner. Advances in technologies, such as electronic health records (EHRs), smartphones {Chow, 2015 #475; Neubeck, 2015 #474; Hamilton, 2018 #473}, and wearable sensors {Martin, 2015 #479; McConnell, 2017 #478; Guo, 2019 #477; Perez, 2019 #476} may have prognostic implications beyond the conventional in-office clinical assessment. However, prior studies leveraging these technologies have focused on either (1) prognosis, which is often not transferable across health systems, or (2) automated risk reduction, which delivers simple therapies at scale with few personalized factors.

Current digital health endeavors have not had major successes yet for reasons including: (1) risk-averse investments; (2) key problems unaddressed, (3) lack of synergy between companies and healthcare; (4) misaligned financial incentives across patients, providers, payers, and companies; (5) the change-averse cultures and complex internal relationships of healthcare systems; (6) data interoperability that requires a long development cycle; and (7) healthcare distribution that is currently enterprise-facing and not consumer-aligned.

The present pandemic has placed significant strains on the link between clinicians and patients highlighting the need for rapid innovation for virtual care.

The primary goals of the present proposal are to demonstrate feasibility of this novel platform, to assess if the DMP can be feasibly implemented prior to hospital discharge for patients hospitalized for heart failure. This is a first necessary step before testing efficacy in a large multi-center study.

Description of AstraZeneca Platform

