AstraZeneca has proposed a Disease Management Platform (DMP) to be used across multiple disease indications to provide a unified experience for the management of patients throughout their patient care journey. This DMP will integrate multiple systems, including a patient App where patients can enter mood, symptoms, weight measures, vital signs such as blood pressure (BP) and medication adherence. This input will feed directly to a clinician dashboard that will allow the clinical care team access to a real-time view of the patient's state both in and out of the clinic. An evidence generation study in patients with Heart Failure (HF) can be used to assess the implementation of the DMP in patients with HF discharged from the hospital.

AstraZeneca suggests the platform proposes to transform cardiovascular medicine by: (1) focusing on transformative development instead of just testing off-the-shelf solutions; (2) working with complex patients and data at an academic medical center who is invested in healthcare transformation; (3) amassing a diverse team of experts in cardiovascular medicine, investigation, engineering, and strategy; (4) focusing on the specific issue of HF, where current healthcare system strains are non-viable for patients, providers, and payers; and (5) improving the healthcare experience for both patients and healthcare professionals.

Patient Smartphone App

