- **Historical MGH control population:** Patients 21 years and older with a diagnosis of HF admitted to MGH cardiology services (Ellison 10 and 11) admitted in the year prior discharged home. Matched 1:2 based on age, sex, HFrEF(<40%), HFmEF(40-49%) HFpEF(≥50%), CAD, T2D, month admitted (minus 1y), number of prior 12mo hospital admissions.
- **Contemporaneous BWH control population:** Patients 21 years and older with a diagnosis of HF admitted to BWH cardiology services admitted during intervention study population enrollment and discharged home. Matched 1:2 based on age, sex, HFrEF(<40%), HFmEF(40-49%) HFpEF(≥50%), CAD, T2D, month admitted, number of prior 12mo hospital admissions.
- **Historical BWH control population:** Patients 21 years and older with a diagnosis of HF admitted to BWH cardiology services admitted in the year prior discharged home. Matched 1:2 based on age, sex, HFrEF(<40%), HFmEF(40-49%) HFpEF(≥50%), CAD, T2D, month admitted (minus 1y), number of prior 12mo hospital admissions.

Inclusion Criteria

- Adults (>21 years) admitted to MGH Cardiology services (Ellison 10 and 11) with a diagnosis of acute or chronic heart failure [HFrEF(<40%), HFmEF(40-49%) HFpEF(≥50%)] (or to BWH Cardiology services for BWH EHR-based controls)
- Has a smartphone or iPad and is willing to enter health metrics into DMP App and email willing to use for the study
- Access to the internet
- Established or with plan to establish primary cardiologist at MGH (or at BWH for BWH EHR-based controls)
- Discharged home or to self-care (with or without home services)

Exclusion Criteria

- Moderate or severe cognitive impairment
- Non-English-speaking
- Palliative management only (comfort measures)
- Does not own a smartphone or iPad (not considered for EHR-based controls)
- Incarcerated
- Enrolled in study with similar outcomes

Study Outcomes

Primary: To test the feasibility of implementing the AMAZE™ disease management platform intervention after in-patient heart failure hospitalization and patient perceived value of the AMAZE™ disease management platform. The feasibility will be measured using conversion rate (percent of patients approached who enroll on the disease management platform). The perceived value will be measured using the participants mHealth App Usability Questionnaire (MAUQ) score.

Exploratory: The following exploratory outcomes will be measured as follows:

1. Heart failure symptom changes using the Kansas City Cardiomyopathy Questionnaire (KCCQ).

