 - a. Heart failure symptoms will be measured as the changes in KCCQ scores between the 30 day and 60 day time-points.
2. Patient daily log compliance.
 - a. Daily log compliance will be measured after 60 days using the total number of days patient completes daily log in the AMAZE™ app out of total days patient is enrolled in the app.
3. Patient app usage.
 - a. Patient app usage will be measured as the number of days the patient engages (i.e. completes daily log, sends a message) with the app at least once a day during the study period.
4. Patient app messaging.
 - a. Patient app messaging will be measured as the number of messages sent by the patient during the 60 day study period.
5. Changes in hospital readmissions.
 - a. Hospital readmission rates in the enrolled study group will be compared to readmission rates in historical control groups.
6. Use of ancillary healthcare resources.
 - a. Rates ancillary healthcare resources (i.e. emergency room visits, urgent care visits, unexpected ambulatory care visits, cardiac rehab) in the enrolled study group will be compared to rates of usage in a historical control group.

Subject Enrollment

Overview

Approximately 70 patients will be enrolled in the study. Patients admitted to MGH cardiology will be screened by study staff for inclusion/exclusion criteria. Study staff will obtain approval to approach eligible patients by the inpatient clinical team. Approximately 2-days prior to discharge, suitable patients will be consented and onboarded with study staff, with the technical support available 24/7 via email or phone through BrightInsight, Inc.

Procedure for obtaining informed consent

We will use Mass General Brigham electronic resources to identify and screen patients for the eligibility criteria listed above. Our internal (MGH) data and analytics team developed an automated process to screen and extract a list of eligible admitted patients on Ellison 10/11 through Research Patient Data Registry (RDPR) and Enterprise Data Warehouse (EDW) (IRB Protocol # 2020P002432). The list will be sent to the study staff daily; study staff will perform chart review of participants on the list to confirm eligibility.

We will focus on patients with a diagnosis of heart failure, who speak and read English.

We will also use the attached study flyer to advertise the study to patients on inpatient floors, with nurse manager approval for the respective floors.

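### The aims speak of heart failure hospitalizations, but eligibility and control matching ignore the reason for admission, so the enrolled group may be broader than the conclusions name and the exploratory control comparisons are open to confounding

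*Combined protocol and SAP*

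**What the plan says.** **Population named in the aims.** Specific Aim 1 (section I), repeated as the primary outcome under Study Outcomes (section III), is to test the "feasibility of implementing the AMAZE™ disease management platform intervention after in-patient heart failure hospitalization". The primary goal in section II is "to assess if the DMP can be feasibly implemented prior to hospital discharge for patients hospitalized for heart failure".

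**Population named elsewhere.** The platform description in section II is wider and gives no reason for admission: "implementation of the DMP in patients with HF discharged from the hospital".

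**Operative criteria.** The Inclusion Criteria in section III ask for "Adults (>21 years) admitted to MGH Cardiology services (Ellison 10 and 11) with a diagnosis of acute or chronic heart failure", with an ejection-fraction class. The intervention population statement just before them also asks only for an HF diagnosis and a cardiology admission. The other criteria concern device, email and internet access, an MGH cardiologist, home discharge, language, cognition, palliative status, incarceration and competing studies. None concerns why the patient was admitted. The consent procedure describes the screening focus in the same terms: "We will focus on patients with a diagnosis of heart failure, who speak and read English".

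**Controls.** Each of the three control groups (historical MGH, contemporaneous BWH, historical BWH) is defined by an HF diagnosis plus a cardiology admission with discharge home. Each is matched 1:2 on age, sex, ejection-fraction class and, in the contemporaneous BWH version, "CAD, T2D, month admitted, number of prior 12mo hospital admissions". The historical groups use the same list with the month shifted by one year.

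**The concern.** A patient with stable chronic HF who is admitted to cardiology for an arrhythmia, a coronary event or a planned procedure can satisfy every listed criterion. Two consequences follow.

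First, conversion rate and the mHealth App Usability Questionnaire (MAUQ) score would be reported as feasibility and perceived value after an HF hospitalization, although they may come from a mixed group. Willingness to take up an HF self-monitoring app could plausibly differ between someone just treated for decompensation and someone admitted for another problem. Section II presents the pilot as preparation for a large multi-center efficacy study. A conversion rate from an unknown mix is harder to use for planning, and no breakdown by reason for admission is foreseen.

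Second, readmission and use of other services could also depend on the reason for the index admission. If that reason is distributed differently in the enrolled patients and the controls, the groups can differ with no platform effect at all.

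**Working it through.** **1. Is there a figure in the plan to reproduce?** Not on this point: the documents give no share of HF-caused admissions and no readmission rates. The only calculated figure is the power for KCCQ change in section VI. With n = 70, a 0.40 SD change, a paired t-test, two-sided alpha 0.05 and no dropout (the last three assumed), power is 0.910, so the claim of more than 80% reproduces. That figure does not bear on eligibility or matching.

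**2. Target against criteria.**

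| Place | Must HF be the reason for admission? |
|---|---|
| Aim 1 and primary outcome | Yes, on a natural reading |
| Primary goal, section II | Yes |
| Platform description, section II | No |
| Intervention population and Inclusion Criteria, section III | No; chronic HF is named explicitly |
| Screening and chart review | No filter beyond the listed criteria is described |
| Three control definitions | No |
| Matching factors | Not included |

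The criteria therefore define a set that contains the target and may be larger. If a share s of those enrolled was admitted for another reason, 70 × s patients lie outside the named population: 0 at s = 0, 14 at s = 20%, 35 at s = 50%. These values of s are assumptions.

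**3. Can the mix differ between enrolled patients and controls?** The broad definition is common to both, but the routes into the groups are not. Enrolled patients need clinical-team and nurse approval, are approached about two days before discharge (with a remote route for those missed), and must consent. Controls pass none of these steps. MGH patients come from two named floors, whereas BWH controls come from cardiology services with no unit named. Historical controls come from the year before. Any of these could shift the mix. The documents do not show that any of them does.

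**4. Size of the confounding.** Let h_E and h_C be the shares of HF-caused admissions in enrolled patients and controls, and r1 and r0 the readmission risks after HF-caused and other admissions. With no platform effect,

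expected difference = (h_E − h_C) × (r1 − r0).

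Assume r1 = 25% and r0 = 10% to 20%, so that r1 − r0 is 5 to 15 points:

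| Difference in mix | Spurious difference in readmission |
|---|---|
| 0 points | 0 |
| 20 points | 0.20 × (5 to 15) = 1 to 3 points |
| 40 points | 0.40 × (5 to 15) = 2 to 6 points |

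For example, with r0 = 15%, h_E = 50% and h_C = 70%: enrolled 0.5 × 25 + 0.5 × 15 = 20%; controls 0.7 × 25 + 0.3 × 15 = 22%. The sign reverses if the mix is reversed.

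**5. In proportion to sampling error.** With 70 enrolled and 70 × 2 = 140 controls in one group, rates of 20% and 22%, and matching ignored, the 95% half-width is 1.96 × √(0.20 × 0.80/70 + 0.22 × 0.78/140) = 1.96 × √(0.002286 + 0.001226) ≈ 11.6 points. The illustrated bias runs from under a tenth of that (1 point) to about half of it (6 points).

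**The case against.** The strongest case on the other side is that broad eligibility looks deliberate. The criterion names chronic HF, the platform description uses the wider wording, and for a single-arm feasibility pilot of an HF app it is defensible to enrol any cardiology inpatient with HF. On this view only some loose wording needs correcting. Controls share the same definition, and the historical MGH group comes from the same floors in the same calendar month. Bias therefore needs a difference in mix for which the documents give no evidence, and any plausible amount is small beside the sampling error of an explicitly exploratory comparison.

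Much of this stands. It is a good reason to leave eligibility alone and change the aims instead. It does not remove the mismatch in wording. Nor does a shared definition guarantee a shared mix once approval, consent and a different hospital or year come between.

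The screening algorithm belongs to a separate protocol (2020P002432) that was not supplied. It might select HF admissions, but nothing here says so, and if it does the criteria should state it.

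A reader might infer more: that the enrolled population is a different one from the target, or that the control comparisons are biased. The documents support neither. The enrolled population includes the target, the overlap could be nearly complete, and the bias is zero if the mix is equal.

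**Conclusion.** The point holds as a gap in wording and matching, not as a demonstrated bias. The aim, primary outcome and goal name a narrower population than the criteria admit. No control definition or matching factor uses the reason for admission.

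For conversion rate and MAUQ, which have no control group and no stated success threshold, the issue is labelling and generalizability. It would be wrong to read it as making those estimates invalid.

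For readmission and resource use, the stated matching leaves a source of confounding open. Its size cannot be determined from the documents. The range of 1 to 6 points rests wholly on the assumed risks and assumed mix differences of 20 or 40 points. Because these comparisons are exploratory and the correction is cheap, this is a worthwhile improvement and does not threaten the trial's main result.

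**What to change.** Keep eligibility as it is and make four changes.

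1. Reword Aim 1, the primary outcome and the section II goal so that they refer to cardiology inpatients with a diagnosis of heart failure.
2. Record from the EHR, for every enrolled patient and every control, whether HF was the principal reason for the index admission. Diagnoses are already taken from the record for participants. Control data come from RPDR, with chart review allowed.
3. Add this variable as a matching factor, or as an adjustment variable, in all three control comparisons.
4. Record it in the pre-screening log for everyone approached, including those who decline. The conversion rate has all approached patients as its denominator, so it cannot be split by reason for admission without the decliners. Report the split descriptively. Give MAUQ by reason as a descriptive summary only, since one subgroup could be small (14 patients if the share were 20%).

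The cost is a short amendment, one extra variable, slightly harder matching, and a small change to what is collected and kept for screened patients. The consent procedure now plans only age, sex and race/ethnicity for the recruitment analysis, and only these are kept once identifiers are stripped. Accrual is unaffected.

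If the sponsor instead restricts eligibility to HF admissions, the same restriction must apply to the controls. The matching factor and the split reporting are then not needed, because the variable would be constant.

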We will create a database of potentially eligible subjects and contact their nurses to confirm eligibility and that they are suitable for the study. We will also verify that the nurse approves of a coordinator approaching their patient. A study coordinator will approach approved and eligible patients to introduce the study. The study coordinator will then review the consent form and study procedure and obtain written consent from the patient. Study coordinators will use an iPad to go over the consent form with the patient. The subject and the study coordinator will sign electronic copies of the consent form using Adobe eSign. Adobe and the iPad will be used whenever possible, but subjects also may be consented with a paper consent form. Subjects will be sent a copy of the consent form via email from Adobe, which automatically sends a pdf copy of the signed consent form to all parties, or they will be sent a scanned paper copy via the Partners send secure system. Subjects with any cognitive disability that prevents them from consenting for themselves will also prevent them from using the AMAZE application. Therefore, subjects who cannot consent for themselves will be excluded from the study. Staff will clearly explain that participation in the study is voluntary and the subject can choose to withdraw from the study at any time.

We will approach patients who are interested in joining the study but are transferred to other inpatient units for various reasons (procedures etc.) at their new location if permitted by their care team. We will verify that the patient is still interested in joining the study before consenting and onboarding them.

If we are unable to consent and/or onboard patients to the study while they are in the hospital, we will schedule a time to do so remotely using Partners Healthcare Enterprise Zoom once they have been discharged. In such cases, we will aim to enroll the patient within three days of being discharged from the hospital. With their consent, we will mail them their study devices: a blood pressure cuff and home scale. Patients can also refuse the study when talking to the research coordinator.

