Heart Rate greater than	>100 bpm	once
Heart Rate less than	<60 bpm	once
Log Compliance	< 1 entry	Over 5 days

Participants will be asked and encouraged to enter information into the App daily. Information that will be entered into the App include:

- Physical well-being – How are you feeling today? [bad, okay, good]
- Medications – Have you taken all of your medications for heart failure today? [yes, no]
 - Medication list will be auto populated in the DMP App as part of the EPIC integration process. The list the patient can see in the HF DMP App will mimic what is in Patient Gateway.
- Symptoms – What symptoms do you have today? [cough, difficulty sleeping flat, dizziness, fatigue, leg/ankle/foot swelling, loss of appetite, shortness of breath, weakness, none of these]
- Activity – How active were you today? [Mild - none or <5 minutes, Moderate – 6 to >30minutes]
- Biometrics – weight, blood pressure, heart rate
- Kansas City Cardiomyopathy Questionnaire (see attachment) at 30-and 60-days

Participants without access to a home scale and/or blood pressure monitor to measure weight and blood pressure will be provided with device(s) purchased by the research study fund. Participants receiving a device will be able to keep the device(s) once the study has ended.

Participant Education Objectives and Outline

The educational components of this pilot study aim to provide key facts to individuals (and family) diagnosed with heart failure, to aide in their ability to stay active and well. Our education will focus on medication adherence, symptom recognition and management, communicating to your care team and lifestyle habits that can contribute to healthy living.

1. Participants will be able to identify the most common symptoms related to heart failure and recognize the importance of sharing specific changes in these symptoms to their doctor or care team or nurse navigator; to help with management and optimization of their disease.
2. Participants will become familiar with the names of their heart failure medications, maintain an accurate list of the medications and doses and co-create actions to ensure they take these medications daily.
3. Participants will gain knowledge about safe, regular activity and food choices that can impact their weight and heart failure symptoms.

Data Collection and Surveys

See “Study Schematic” Section for a visual overview of the study.

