Patients will be surveyed for baseline demographics and study outcomes. Medical history, including labs, procedures, and diagnoses will be collected from the medical record and recorded in REDCap

At consent, subjects will be surveyed for demographics that cannot be obtained from the medical record (See “Baseline Demographics” attachment).

Quality of life will be collected through the patient-facing AMAZE app (See “KCCQ” attachment). Patient satisfaction will be collected through MAUQ (attached) administered through the app. The app will also track patient medication adherence, and facilitate symptom, blood pressure, weight, and activity tracking.

At roughly 30 days from enrollment and again at 60 days from enrollment, a research coordinator will call the patient to collect 1) current cardiac medications and any changes to medication regimen and 2) hospitalizations, ED presentations, urgent care visits, primary care or cardiology visits, and cardiac rehab enrollment at institutions outside MGB. Research coordinators will review subject medical records to determine these events at MGB.

EHR data for the control populations (MGH and BWH) will be obtained from RPDR. We may also review medical records for these patients to collect/confirm EHR data.

Optional interviews

Two rounds of interviews regarding the user experience of the AMAZE app may be conducted over the course of the study. The interview questions ask about usability and helpfulness of the app, along with the option to give feedback about technical issues and features that could use improvement. These interviews

are optional and do not affect the participants' overall participation in the study. This is reflected in the consent form, with a section allocated to participants' choice of whether they would like to be contacted for these interviews or not.

Participants who consent to being contacted for the interviews will be selected based on engagement with the app. We will measure engagement by percentage of daily log compliance over the past seven days. Participants who fill out the daily log more than half the days in a week will be classified as "engaged with the app" and those who fill out the daily log less than half the days in a week will be categorized as "disengaged with the app."

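### Daily log compliance (exploratory outcome 2a) counts days in hospital in its denominator, so it may not describe logging after discharge

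*Combined protocol and SAP*

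**What the plan says.** Section III, Study Outcomes, exploratory item 2a defines the measure: "Daily log compliance will be measured after 60 days using the total number of days patient completes daily log", taken "out of total days patient is enrolled in the app". No inpatient day is excluded there or elsewhere.

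There are two onboarding routes. The default is in Subject Enrollment, Overview: "Approximately 2-days prior to discharge, suitable patients will be consented and onboarded with study staff". For patients who cannot be onboarded in hospital, the consent procedure provides a remote route: "we will aim to enroll the patient within three days of being discharged from the hospital".

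The follow-up clock runs from enrolment, not discharge. Data Collection and Surveys places the coordinator calls "At roughly 30 days from enrollment and again at 60 days from enrollment". Those calls ask about hospitalizations outside the health system, and chart review covers those inside it. The section does not mention admission dates, discharge dates or length of stay.

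On logging itself, Study Procedures says "Participants will be asked and encouraged to enter information into the App daily", with no exception for time in hospital.

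Optional interviews uses the same measure over a shorter window: "We will measure engagement by percentage of daily log compliance over the past seven days". Logging on more than half the days makes a participant engaged, and on less than half, disengaged.

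**The concern.** The study is framed around patients who have gone home. Section II describes implementation in patients discharged from hospital, Aim 1 concerns the period after the admission, and Section V speaks of learning about compliance once patients have left. A denominator that includes hospital days does not match that purpose.

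Two kinds of hospital day enter, for different reasons. Index-stay days enter because default onboarding comes before discharge; patients onboarded remotely have none, so the two routes are measured over different kinds of day. Readmission days enter for any patient, however onboarded, because nothing excludes them.

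If patients log less while in hospital, the reported figure mixes willingness to log with time spent in hospital, and it falls furthest for readmitted patients. The 7-day engagement class would be affected in the same way for anyone in hospital shortly before a call.

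**Working it through.** The plan states no figure for log compliance, so there is none to reproduce.

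**Inputs from the protocol**
- Observation period: 60 days from enrolment (outcome 2a; Data Collection and Surveys).
- Index inpatient days after onboarding, h: about 2 for the default route, 0 for the remote route.

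**Inputs assumed, because the documents give none**
- Home logging rate, c: 70%, range 50% to 90%.
- Inpatient logging rate, q: 0 as the base case, then varied.
- Readmission days, L: 6 per readmitted patient, with 20% readmitted. Range: 5 to 7 days, 10% to 30% readmitted.

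**Formula**

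Compliance as defined = [c × (60 − h − L) + q × (h + L)] / 60.

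Compliance over days out of hospital = c.

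Shortfall = (c − q) × (h + L) / 60.

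The sign depends only on whether c exceeds q. The size depends on the hospital days counted.

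**Shortfall with no inpatient logs (q = 0), in percentage points**

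| Case | Hospital days counted | c = 50% | c = 70% | c = 90% |
|---|---|---|---|---|
| Index stay only | 2 | 1.7 | 2.3 | 3.0 |
| Default route plus 6-day readmission | 2 + 6 = 8 | 6.7 | 9.3 | 12.0 |
| Remote route plus 6-day readmission | 0 + 6 = 6 | 5.0 | 7.0 | 9.0 |
| Cohort mean, all default route, 20% readmitted | 2 + 0.20 × 6 = 3.2 | 2.7 | 3.7 | 4.8 |

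For example, 0.70 × 8 / 60 = 9.3 points and 0.70 × 3.2 / 60 = 3.7 points.

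**Sensitivity**
- Readmission assumptions: the cohort mean runs from 0.50 × (2 + 0.10 × 5) / 60 = 2.1 points to 0.90 × (2 + 0.30 × 7) / 60 = 6.2 points.
- Onboarding route: if every patient were onboarded after discharge, the 3.7 would fall to 0.70 × 1.2 / 60 = 1.4 points.
- Inpatient logging at half the home rate: every shortfall halves, so 9.3 becomes 4.7.
- Inpatient logging equal to the home rate: the shortfall is zero.
- A log on every inpatient day: for the index stay alone the measure reads (0.70 × 58 + 2) / 60 = 71.0%, which is 1.0 point above the home rate.

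**The 7-day class.** A patient in hospital for 4 of the 7 days who does not log there can reach at most 3/7 = 43%. That is below half, so the patient is classed as disengaged even with a log on every day at home.

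**The case against.** The protocol defines compliance over enrolled days and asks for a log every day without exception. Most items (well-being, symptoms, activity, whether medicines were taken) can be answered on a phone in a hospital bed, and nothing says that a log without biometrics is incomplete. Section II also makes implementation before discharge a feasibility goal, so counting those days is defensible. This stands: the all-days figure is a legitimate measure and should be kept.

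A reader might infer that home compliance is understated as a matter of fact. The documents do not support that, because no section says that patients log less in hospital than at home. A reader might also blame early onboarding for the whole effect. It accounts only for the index days, about 2; readmission days would count whatever the onboarding time.

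A reader might further infer that a planned analysis of logging against readmission is compromised. None is planned. Under outcome 5, "Hospital readmission rates in the enrolled study group will be compared to readmission rates in historical control groups". A link between low logging and readmission would be partly built in only if someone later looked for one.

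The consequences are also limited. Outcome 2a has no threshold, test or comparator. The 7-day class only selects optional interviewees, and at the 30- and 60-day calls index-stay days will normally lie outside the window. Against that, each group of five interviewees includes only one disengaged participant, so a single misclassified patient could supply that group's whole disengaged view.

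**Conclusion.** The point holds as a minor one. Outcome 2a includes hospital days by its stated rule, and that rule fits poorly with a study of patients after discharge. Whether the result understates logging after discharge is conditional: it does if inpatients log less, it does not if they log equally, and it overstates if they log more.

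At an assumed 70% home rate with no inpatient logs, the loss is about 2.3 points for the index stay alone and 9.3 points with an assumed 6-day readmission. The cohort mean loss is about 3.7 points if an assumed 20% are readmitted and all are onboarded 2 days before discharge. Taking the full share of days, 2/60 = 3.3, 8/60 = 13.3 and 3.2/60 = 5.3 points, would be too strong, since those losses arise only if patients log on every day at home and never in hospital.

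The average effect is modest. The effect on an individual readmitted patient can be appreciable.

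**What to change.** Keep the all-days figure in 2a and report beside it compliance over days out of hospital:

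- Start the count at the later of the day after discharge and the day of onboarding. Starting every patient on the day after discharge would be wrong for the remote route: someone onboarded on day 3 would be charged with 2 days before having the app, and 2/60 = 3.3%.
- Remove inpatient days from both numerator and denominator. State whether days of admission and discharge count as inpatient.
- Record admission and discharge dates when hospitalizations are taken from the health system's records and at the 30- and 60-day calls.
- Apply the same rule to the 7-day engagement class. With 7 days, exactly half cannot occur; with fewer days it can (2 of 4, say), so assign that case, and say what happens when no days remain.

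The cost is a short addition to the outcome definition and two date fields. Dates for stays elsewhere rely on patient report. The added figure discards logs made in hospital and has a denominator that differs between patients, which is why the all-days figure should stay beside it.
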